**Physician's Office will complete this section:**

1. Date patient started protocol treatment \_\_\_\_\_  
Date patient was removed from study \_\_\_\_\_
2. Patient's planned daily dose \_\_\_\_\_  
Total number of pills taken this month \_\_\_\_\_

Physician/Nurse/Data Manager's Signature \_\_\_\_\_

## The Low Iodine Diet

### What is Iodine?

Iodine is a mineral. It plays an important role in several processes that take place in the body. One is the production of a hormone called thyroxine, which occurs in the thyroid gland.

### Where is Iodine Found?

The amount of iodine found in food varies. Much of the iodine we get comes from iodized salt and breads. Adults need 150 micrograms of iodine a day. This booklet describes a low iodine diet. This is a diet with less than 50 micrograms of iodine per day.

### Why is a Low Iodine Diet Necessary?

The iodine in your diet can block the uptake of radioactive iodine by the thyroid gland. Your doctor could put you on a low iodine diet one or two weeks before you get the radioactive iodine. Stay on this diet until your test or treatment is complete. Your doctor will tell you when to begin and when to stop this diet. If you have any questions, speak with your doctor. You may also see a dietitian if necessary. If you have any questions about your diet, call [contact] to speak to a dietitian.

### What Should You Avoid?

Read all food labels to check for iodine content. Do NOT eat or use:

- Iodized salt.
- Sea salt in any form.
- Onion salt.
- Celery salt.
- Garlic salt.
- Seasoned salt.
- Kelp (seaweed).
- Any food that has:
  - Iodates
  - Iodides
  - Algin
  - Alginates
  - Carrageen
  - Agar
- Commercial breads and bakery products because they often contain iodate.
- Milk (except for 1 ounce a day), eggs, and seafood.
- Vitamins and food supplements if they have iodine. If you have any doubt, do not take them.
- Food, pills, or capsules with food dyes or that are orange, red, or brown in color. Examples include red or pink cereals or candies.
- Antiseptics, such as tincture of iodine (Betadine®) applied on a cut.
- Cough medicines (especially those with red coloring).
- Supplements such as:
  - Ensure®
  - Boost®
  - Commercial shakes
  - Nutrament®
- Restaurant and processed foods, because they are often high in iodine content.
- Soy products such as edamame, tofu, soy burgers (e.g., Boca®), etc.

- All canned foods, because the lining of the can contains iodine.

Do not stop taking any of your medicines unless your doctor tells you. If you are receiving tube feeding formula, ask your dietitian or doctor what to do. This low iodine diet does not meet the suggested daily allowance for all nutrients. You will be on it for a short time only.

#### Drink Plenty of Fluids

Note: Unless your doctor tells you differently, you must drink at least 8 to 10, 8-ounce cups of fluid a day. This includes the drinks in the diet guidelines and as much water as you want.

### **Low Iodine Diet Guidelines:**

#### **Breads and Cereals**

Total number of servings per day: 6-8  
(1 serving equals 1 slice of bread or 1/2 cup of cooked pasta)

##### Include

Plain cooked barley, oats, millet, buckwheat, bulgur wheat, quinoa; unsalted, unprocessed preservative-free boxed cereals such as puffed rice and shredded wheat; rice, plain macaroni, spaghetti, noodles; cream of rice or cream of wheat hot cereals; unsalted rice cakes, unsalted plain matzah, English muffins, plain unsalted popcorn, homemade breads prepared without commercial dough.

##### Avoid

All commercial breads and rolls, processed boxed cereals, salted crackers, potato chips, pretzels, bagels, bialys, Melba toast, all other crackers, egg noodles, packaged rice and pasta mixes.

#### **Meat and Meat Substitutes**

Total number of servings per day: Two–three  
(1 serving equals 3 ounces of meat, fish, poultry, or 2 Tablespoons of unsalted peanut or almond butter)

##### Include

Fresh beef, veal, pork, lamb, chicken and turkey; unsalted peanut or almond butter; fresh-water fish such as carp, river bass, lake trout, and river perch; fresh egg white.

##### Avoid

Egg yolks and whole eggs, foods made with eggs; all fast foods; all canned fish such as salmon and tuna; seafood, shellfish (clams, crabs, oysters, lobsters), or any food made with fish stock; all processed meats; liver and all organ meats; all canned, dried, salted, or cured meats such as bacon, sausage, ham, frankfurters, chipped beef, luncheon meats (salami, bologna, pastrami); spicy meats such as chili, beef jerky, liverwurst; all canned or processed poultry such as turkey or chicken roll; tofu and soy products, such as soy burgers (e.g., Boca); salted peanut butter.

#### **Milk and Milk Products**

Total number of servings per day: Zero

##### Include

None allowed

Exception: Only 1 ounce of milk a day in your coffee or tea.

**Avoid**

All milk (except for one ounce daily) and milk products such as condensed or evaporated milk, cheese, yogurt, puddings, ice cream, custard; any cream such as heavy or light cream, whipped cream, sour cream; any foods made with cream or milk or cheese such as cream soup, pizza, macaroni and cheese.

**Fruits**

Total number of servings per day: Five  
(1 serving equals 1 small piece of fruit or 3/4 cup of juice)

**Include**

All fresh fruit, exception: limit bananas to 1 serving per day; fresh apple sauce; all natural frozen fruits; fresh fruit juices (including bottles or cartons of fruit juice without artificial coloring or preservatives); white grape juice.

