1. Placebo or selumetinib 75 mg orally twice daily will be started on Week 1, Day 1 and continued through 2 days after therapeutic I therapy has been administered. Ideally, placebo or selumetinib dosing/treatment should be maintained for at least 7 days prior to and throughout administration of therapeutic I (this is not a requirement). Extending the time on placebo or selumetinib (i.e. extending time on treatment and/or instituting treatment interruptions) and/or rescheduling/repeating study assessments/procedures/treatments (though therapeutic I should be administered only once) is/are allowed to fulfill the criteria discussed above at the investigator's discretion. The period of time on placebo or selumetinib (i.e. extending time on treatment and/or instituting treatment interruptions) is not to exceed 8 weeks.
2. Patients should adhere to a low iodine diet for 5 days prior to the start of Thyrogen™-stimulated administration of therapeutic I processes. The low iodine diet will be continued through 1 day after I is given. Please see Appendix III for details of the low iodine diet.
3. Thyrogen™ 0.9 mg IM will be administered once daily for 2 consecutive calendar days, with the last dose given 1 calendar day prior to I ingestion.
4. These Adverse Event assessments are meant to denote that study placebo or drug adverse events should be monitored throughout the treatment. No formal visits are required for these assessments, with the exception of Week 3, which is a mandatory visit.
5. Patients <70 years of age will be treated with 150 mCi I (+/- 5 mCi). Patients ≥70 years of age can be treated with a I activity from 100 mCi up to and including 150 mCi (+/- 5 mCi for 100 mCi or 150 mCi administered activities); for these patients, the activity to be

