#### **Metabolism -**

Cytochrome P450 3A4 is the predominant isoform responsible for selumetinib oxidative metabolism with CYP2C19, CYP1A2, CYP2C9, CYP2E1, and CYP3A5 involved to a lesser extent. Its active metabolite, N-desmethyl selumetinib is approximately 3-5 times more potent than selumetinib, and generated primarily by CYP1A2, CYP2C19, CYP2C9 and CYP2C8 and metabolized through the same routes as selumetinib.

**Special Populations** – Renal impairment is expected to have minimal effect on exposure to selumetinib. Patients with moderate and severe hepatic impairment may experience higher exposures of approximately 1.5-and 3-fold, respectively. It is recommended that investigators take this information into consideration if patient experience moderate or severe hepatic impairment during the study treatment.

15.16 **Potential Drug Interactions:** High vitamin E doses may potentiate the anticoagulant activity of warfarin. Monitor PT/INR more frequently in patients receiving both selumetinib and warfarin.

The concomitant intake of supplemental vitamin E should be avoided in all subjects receiving selumetinib.

Avoid co-administering selumetinib with medicinal products that are strong inhibitors of CYP3A4 (eg, clarithromycin, grapefruit juice, oral ketoconazole) and CYP2C19 (eg, ticlopidine). If co-administration is unavoidable, patients should be carefully monitored for AEs. No dose adjustment is necessary for

use of selumetinib with moderate CYP3A4 or CYP2C19 inhibitors. Patients should be carefully monitored for AEs when co-administered with moderate CYP3A4 or CYP2C19 inhibitors.

Avoid concomitant use of strong CYP3A4 inducers (eg, phenytoin, rifampicin, carbamazepine, St. John's Wort) or moderate CYP3A4 inducers with selumetinib.

Selumetinib may be an inhibitor of OAT3 and the potential for a clinically relevant effect on the PK of concomitantly administered substrates of OAT3 cannot be excluded.

Based on *in vitro* data and SimCYP simulations, selumetinib is considered unlikely to cause clinically significant drug-drug interaction via inhibition or induction of CYP enzymes

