#### 15.19 **Nursing Guidelines**

- 15.191 Medication should be taken on an empty stomach with no food or drink other than water for 1 hour before and 2 hours after dosing.
- 15.192 Gastrointestinal side effects were the most commonly reported side effects with this agent (including nausea, diarrhea, constipation, dyspepsia and vomiting). Manage symptomatically and assess for effectiveness of intervention.
- 15.193 Patients experienced acneiform rash. Instruct patient to report this rash and manage symptomatically.
- 15.194 Dyspnea has been reported. Instruct patient to report any shortness of breath to the study team. Rarely interstitial lung disease has been seen with agent.
- 15.195 Hypertension has been seen. Assess blood pressure according to study requirements.
- 15.196 Instruct patients to report any limb swelling (usually legs) to the study team. Rarely LVEF dysfunction has been seen.
- 15.197 Monitor LFT's.
- 15.198 Monitor CBC w/diff. Instruct patients to report any unusual bruising or bleeding to the study team.
- 15.199a Patients may experience increased fatigue. Instruct patients in energy conserving lifestyle.
- 15.199b Warn patients of possible alopecia.
- 15.199c Instruct patients to report any blurred vision or periorbital edema to the

study team.

15.199d Assess patient's concomitant medications as there are numerous drug to drug interactions.

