### INSTRUCTIONS TO THE PATIENT:

1. Complete one form for each 28-day cycle.
2. You will take your dose [ \_\_\_\_\_ mg ( \_\_\_\_\_ 25 mg pills)] TWICE each day (for a total dose of \_\_\_\_\_ mg per day) beginning on Week 1, Day 1 and continued through 2 days after therapeutic  $^{131}\text{I}$  therapy has been administered. It is recommended to take selumetinib (or placebo) on an empty stomach (1 hour before or 2 hours after a meal), approximately 12 hours apart with a glass of water. (NOTE: Avoid excessive sun exposure and use adequate sunscreen protection if sun exposure is anticipated. Do not take vitamin E or multivitamin supplements that provide a total daily dose in excess of 100% of the recommended daily allowance for vitamin E.)
3. Record the date and the time you took them.
4. If you have any comments or notice any side effects, please record them in the Comments column.
5. Bring your pill bottle and this form to your physician when you go for your next appointment.

Date	Day	Time Taken	Comments	Date	Day	Time Taken	Comments
	1				11		
	2				12		
	3				13		
	4				14		
	5				15		
	6				16		
	7				17		
	8				18		
	9				19		
	10				20		

Date	Day	Time Taken	Comments	Date	Day	Time Taken	Comments
	21				26		
	22				27		
	23				28		
	24				29		
	25				30		

Patient's Signature: \_\_\_\_\_ Date: \_\_\_\_\_

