**Avoid**

Cranberries, all dried fruits, all canned fruits and canned fruit juices; jarred applesauce; cranberry and grape juice, canned or bottled cherries; rhubarb.

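### The low iodine diet leaflet allows fresh fruit juices without excepting grapefruit juice, and the diary does not mention it, although Section 15.16 lists it among strong CYP3A4 inhibitors to avoid with selumetinib (minor).

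*Combined protocol and SAP*

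**What the plan says.** **Drug section.** Section 15.15 identifies CYP3A4 as the main enzyme in selumetinib's oxidative metabolism. Section 15.16 then says to avoid giving the drug with "strong inhibitors of CYP3A4 (eg, clarithromycin, grapefruit juice, oral ketoconazole", among others. Where this cannot be avoided, it asks for careful adverse event monitoring.

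**Diet leaflet (Appendix III).** The permitted fruit list reads "All fresh fruit, exception: limit bananas to 1 serving per day" and goes on to allow "fresh fruit juices (including bottles or cartons of fruit juice without artificial coloring or preservatives". The fruit avoid list includes "cranberry and grape juice, canned or bottled cherries; rhubarb". Grapefruit appears neither there, nor in the general avoid list, nor in the beverage avoid list.

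**When the leaflet applies.** Section 4.0, footnote 2: "Patients should adhere to a low iodine diet for 5 days prior to the start of Thyrogen"-stimulated radioiodine treatment, and "The low iodine diet will be continued through 1 day after" the iodine is given. Footnote 1 continues the capsules through 2 days after the iodine.

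**Diary (Appendix II).** Instruction 2 covers meal timing, sun exposure and vitamin E ("Do not take vitamin E or multivitamin supplements that provide a total daily dose in excess of 100" percent of the daily allowance). It says nothing about grapefruit juice.

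**Dosing around food.** Section 15.191 requires "no food or drink other than water for 1 hour before and 2 hours after dosing".

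**The concern.** Staff are told in Section 15.16 that grapefruit juice should be avoided with selumetinib. Neither of the two patient-held sheets in the review copy passes this on, and one of them permits fruit juice in general. The leaflet does name certain juices to avoid, so a patient checking that list could reasonably conclude that grapefruit juice is acceptable.

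Juice is an ordinary part of this diet. The leaflet sets five fruit servings a day, counts three-quarters of a cup of juice as one serving, and puts orange juice in its sample breakfast.

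What is at stake is avoidable exposure to an interacting drink in patients taking 75 mg twice daily, which Section 1.0 gives as the maximum tolerated dose of the capsule. The statistical design is not at stake.

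**Working it through.** The plan states no figure on this point to reproduce. The check is a comparison of texts, followed by simple counting to show how far the texts overlap in time.

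**1. Texts side by side**

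| Place | Grapefruit juice |
|---|---|
| Section 15.16 | Named as an example to avoid |
| Appendix III, fruits permitted | Fresh fruit juices allowed, no exception |
| Appendix III, fruits to avoid | Cranberry and grape juice named, grapefruit not |
| Appendix III, general and beverage avoid lists | Not named |
| Appendix II, instruction 2 | Not named |
| Sections 7.1 and 15.199d | Address concomitant medications, not foods |

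**2. Length of the diet** (Section 4.0, footnotes 2 and 3)

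- Reading A, 5 days before the first Thyrogen dose: 5 + 2 Thyrogen days + 1 iodine day + 1 day after = 9 days.
- Reading B, 5 days before the iodine, with the 2 Thyrogen days included: 5 + 1 + 1 = 7 days.

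**3. Length of planned dosing** (Section 4.0, table and footnote 1)

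Assume the iodine is given in Week 4, that is on day 22 to 28. Adding 2 days gives 24 to 30 dosing days. The diet ends 1 day after the iodine and the capsules 2 days after. The diet starts at most 7 days before the iodine, well after day 1. Every diet day therefore falls within planned dosing unless dosing is interrupted.

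**4. Share of dosing days on the diet**

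- Lowest: 7 / 30 = 23%.
- Highest: 9 / 24 = 38%.
- Dosing days off the diet: 24 − 9 = 15 to 30 − 7 = 23.
- If treatment runs to the 8-week limit (56 days), the share can fall to 7 / 56 = 12.5%.

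**5. Does the fasting rule close the gap?**

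Two doses a day × (1 h before + 2 h after) = 6 h. This leaves 24 − 6 = 18 h a day in which the dosing rule does not exclude juice.

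Steps 2 to 5 show when the juice could be drunk under the patient sheets. They do not measure how often it would be drunk or what would follow.

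**The case against.** The strongest reply is that this is silence rather than contradiction. Appendix III is a general hospital leaflet about iodine, and being on its permitted list means only that a food is acceptable for its iodine content. It never mentions selumetinib and never recommends grapefruit. The diary lists none of the other interacting agents in Section 15.16 either, and interaction control is given to site staff through Sections 7.1 and 15.199d. The consent form, a natural place for such a warning, was removed from the review copy. Section 15.16 itself allows for monitoring when co-administration is unavoidable. Any rise in exposure could occur only in the selumetinib arm, at most 30 of the 60 patients planned.

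Much of this stands, and it keeps the point small. The diary part is an omission, the consent form may carry the warning, and no clinical effect can be shown from the documents.

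It does not remove the leaflet conflict. The protocol adopts the leaflet for days on which capsules are taken, so its permitted list reaches patients to whom Section 15.16 applies. The monitoring clause covers unavoidable use, and drinking a particular juice is avoidable. A medication review would not reliably pick up a drink. A consent form warning, if there is one, would still leave the diet sheet pointing the other way.

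**Conclusion.** The concern holds as a minor inconsistency in patient-facing text. A patient who follows Appendix III to the letter may drink what Section 15.16 says to avoid, and the diary does not correct this. The overlap is 7 to 9 diet days, about 23% to 38% of 24 to 30 planned dosing days, assuming iodine in Week 4 and no interruption; the share is lower if treatment is extended.

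The number of patients affected and the size of any exposure change are unknown, because the documents give no intake data and no exposure ratio. The finding is limited to the wording of Appendices II and III. It has no bearing on the primary endpoint, the sample size or the analysis.

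**What to change.** 1. **Appendix II, instruction 2:** add a line telling patients not to drink grapefruit juice while taking study capsules. This is the most useful edit, because Section 15.16 applies throughout dosing and the diary covers the days off the diet as well.
2. **Appendix III, fruits permitted:** allow fresh fruit juices except grapefruit juice.
3. **Appendix III, fruits to avoid:** add grapefruit juice. If the sponsor prefers not to alter the institution's leaflet, a short study-specific note attached to it would serve for items 2 and 3.
4. **Optional:** extend the wording to whole grapefruit. This goes beyond Section 15.16, which names only the juice.

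The wording should be the same for both arms, as the trial is double-blind. The cost is two short edits to the leaflet and one line in the diary. No procedure, iodine restriction or analysis changes.

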**Avoid**

Cranberries, all dried fruits, all canned fruits and canned fruit juices; jarred applesauce; cranberry and grape juice, canned or bottled cherries; rhubarb.

**Vegetables**

Total number of servings per day: Four  
(1 serving equals 1/2 cup of cooked or 1 cup raw vegetable)

**Include**

All fresh vegetables except spinach, fresh potatoes without skin, all plain frozen vegetables without added salt, fresh or dried legumes such as lentils and peas.

**Avoid**

All canned vegetables and all canned vegetable juices, fresh or dried beans such as red kidney beans, lima beans, navy beans, pinto beans and cowpeas; canned legumes (such as beans, peas, and lentils); canned soups; sauerkraut, celery; commercially prepared potatoes (e.g. instant mashed potatoes); frozen vegetables with added salt; spinach.

**Fat**

Total number of servings per day:  
Suggest four to six servings a day  
(1 serving equals 1 teaspoon of butter or oil)

**Include**

Unsalted margarine or sweet butter (not more than 1 teaspoon of each per day), oils, vegetable shortening, plain oil and white vinegar dressing.

**Avoid**

Salted nuts and seeds, mayonnaise, commercial salad dressings, and lard.

**Beverages**

Total number of servings per day: No restrictions  
One serving equals 12 ounces of a carbonated beverage or 1 cup (8 ounces) of any of the other beverages listed

**Include**

Water; bottled carbonated beverages without added coloring (such as Sprite®, 7-Up®, sodium-free seltzer); brewed coffee, tea steeped from tea leaves; white tea bags; fresh lemonade or fresh orangeade.

**Avoid**

Mineral water containing sodium; all bottled, canned, or powdered: iced tea, lemonade, instant coffee, instant tea, instant iced-tea, fruit punch, and other powdered or commercial drinks, such as Hi-C® and Kool-Aid®; tea steeped from tea bags; soy milk and rice milk (which contain sea salt); ginger ale, Coke®, Pepsi® or any other carbonated beverages with added coloring.

**Desserts and sweets**

Total number of servings per day: Two

(See below for serving equivalents)

**Include**

Each of the following equals 1 serving:

- 1 cup Knox® clear gelatin
- 2 tablespoons (T) sugar
- 2T Honey
- 2T Maple syrup
- 2 regular size Marshmallows
- 1/2 cup Natural sorbets with no coloring or added salt

**Avoid**

All bakery products such as pies, cakes, pastries, danishes, muffins, donuts and cookies; graham crackers; Jell-O®, colored gelatins; chocolate and chocolate desserts; candy.

**Miscellaneous**

Total number of servings per day: Unlimited

**Include**

Pepper, spices such as cinnamon; herbs such as oregano; white vinegar, and non-iodized salt (contains trace amounts of iodine, use sparingly).

**Avoid**

All salted foods such as salted nuts, Chinese food, soy sauce, catsup, Worcestershire sauce, chili sauce, all commercial sauces, tomato sauce, all gravies, olives, pickles, relish, bouillon cubes, soup bases, iodized salt, sea salt, onion salt, garlic salt, celery salt, seasoned salt, kelp (seaweed); molasses; any food containing food coloring, iodates, iodides, iodate dough conditioners or stabilizers, algin, alginate, carrageens, agar, or nori (seaweed); all sushi; red wine vinegar, balsamic vinegar (with caramel coloring); all additives, preservatives, or artificial colorings.

**Sample Menu for a Low Iodine Diet**

**BREAKFAST**

- 1 Fruit 1/2 cup orange juice
- 3 Breads 1/2 cup oatmeal (no milk)
- 1 plain unsalted matzah
- 1 Meat 1 egg white omelet
- Misc. 2 teaspoons sugar

1 Beverage 1 cup brewed coffee

MID MORNING SNACK

1 Fruit 2 Rice cakes  
1 teaspoon unsalted butter  
1 cup water

LUNCH

1 Meat 3 oz fresh turkey breast  
2 Fats 2 tsp oil  
2 Breads 2 slices homemade white bread  
1 Vegetable 1 cup Romaine lettuce  
1 Beverage 1 cup fresh lemonade

MID AFTERNOON SNACK

1 Fruit 1 fresh apple  
1 Meat 2 tablespoons unsalted peanut butter

DINNER

1 Meat 3 oz roast beef  
2 Breads 1 baked potato (no skin)  
2 Vegetables 1 cup fresh broccoli  
2 Fats 2 tsp oil (used in cooking)  
1 Fruit 1 orange  
1 Beverage 1 cup white tea

BEDTIME SNACK

1 Fruit 1 small pear  
1 Beverage 1 cup tea made from fresh tea leaves

©1997 Memorial Sloan-Kettering Cancer Center  
[name]  
Revised 2002, 2004, 2006, 2008

